6.1.3.2 Other Secondary Efficacy Endpoints

• Leukemia-free survival (LFS)

LFS is defined as the time from the date of first CRc until the date of documented relapse (excluding relapse from PR) or death for subjects who achieve CRc (relapse date or death date – first CRc disease assessment date + 1). For a subject who is not known to have relapsed or died, LFS is censored on the date of last relapse-free disease assessment date (last relapse-free disease assessment date – first CRc disease assessment date + 1).

- Complete Remission with Partial Hematologic Recovery (CRh) Rate
 CRh rate is defined as the number of subjects who achieve CRh at any of the post
 - baseline visits and do not have best response of CR divided by the number of subjects in the analysis population.
- Composite Complete Remission (CRc) Rate

CRc rate is defined as the number of subjects who achieve the best response of CRc (CR, CRp or CRi) divided by the number of subjects in the analysis population.

• Duration of remission

Duration of remission includes duration of CRc (DCRc), duration of CR/CRh (DCRCRh), duration of CRh (DCRh), duration of CR (DCR), and duration of response (DR) (i.e., CRc + PR).

Duration of CRc is defined as the time from the date of first CRc until the date of first documented relapse for subjects who achieve CRc (relapse date – first CRc disease assessment date + 1). Subjects who die without report of relapse are considered non-events and censored at their last relapse-free disease assessment date (last relapse-free disease assessment date – first CRc disease assessment date + 1). Other subjects who do not relapse on study are considered non-events and censored at the last relapse-free disease assessment date.

Duration of CR/CRh is defined similarly as duration of CRc for subjects who achieve either CR or CRh. For subjects who achieve both CR and CRh, the first date will be used as the starting date of the duration.

As a sensitivity analysis, Duration of CR/CRh will be defined similarly as the above, however deaths without report of relapse are considered as events.

Duration of CRh is defined similarly as duration of CRc for subjects who achieve CRh.

Duration of CR is defined similarly as duration of CRc for subjects who achieve CR.

Duration of response is defined as the time from the date of either first CRc or PR until the date of documented relapse (i.e., the date of first NR after CRc or PR) for subjects who achieve CRc or PR (relapse date – first CRc or PR disease assessment date + 1). Subjects who die without report of relapse are considered non-events and censored at their last relapse-free disease assessment date (last relapse-free disease assessment date – first CRc or PR disease assessment date + 1). Other subjects who do not relapse on study are considered non-events and censored at the last response relapse-free disease assessment date.

• Transfusion conversion rate and transfusion maintenance rate

Transfusion conversion rate and transfusion maintenance rate will only be defined for subjects in ASP2215 arm.

For the purpose of defining transfusion conversion rate and transfusion maintenance rate, transfusion status (independent vs. dependent) at baseline period and post-baseline period are defined in the following for subjects who took at least one dose of study drug:

Baseline transfusion status:

 Baseline period is defined as the period from 28 days prior to the first dose to 28 days post first dose. For subjects who are on treatment <28 days, baseline period is from 28 days prior to the first dose until the end of treatment.

 Subjects are classified as baseline transfusion independent if there is no RBC or platelet transfusions within the baseline period; otherwise, the subject is baseline transfusion dependent.

Post-baseline transfusion status (only defined for ASP2215 arm):

- Post-baseline period is defined as the period from 29 days post first dose until last dose.
- For subjects who are on treatment >=84 days, subjects are classified post-baseline transfusion independent if there is one consecutive 56 days without any RBC or platelet transfusion within post-baseline period.
- For subjects who are on treatment >28 days but <84 days, if there is no RBC or
 platelet transfusion within post-baseline period, post-baseline transfusion status is
 not evaluable.
- For subjects who are on treatment <=28 days, post-baseline transfusion status is not evaluable.
- Otherwise, the subject is considered post-baseline transfusion dependent.

Both transfusion conversion rate and maintenance rate are defined for subjects who has evaluable post-baseline transfusion status.

Transfusion conversion rate is defined as the number of subjects who were transfusion dependent at baseline period but become transfusion independent at post-baseline period divided by the total number of subjects who were transfusion dependent at baseline period.

Transfusion maintenance rate is defined as the number of subjects who were transfusion independent at baseline period and still maintain transfusion independent at post-baseline period divided by the total number of subjects who were transfusion independent at baseline period.

As a sensitivity analysis, transfusion conversion rate and transfusion maintenance rate will be defined alternatively by considering all subjects who had not-evaluable post-baseline transfusion status as transfusion dependent.

• Transplantation rate

Transplantation rate is defined as the percentage of subjects undergoing HSCT during the study period.

• Brief fatigue inventory (BFI)

BFI was developed to assess the severity of fatigue and the impact of fatigue on daily functioning in patients with fatigue due to cancer and cancer treatment. The BFI short form has 9 items and a 24-hour recall. A global fatigue score is computed by averaging the scores of the 9 items. Other BFI scores will be derived per PRO SAP.

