- i. Ophthalmologic assessment to be performed by visual acuity measurement and ophthalmoscopy during the screening period, day 1 (± 7 days) of cycle 2, day 1 (± 7 days) of every 2 cycles thereafter, and when clinically indicated. In symptomatic subjects, the ophthalmologic assessment should also include slit lamp biomicroscopy, visual fields performed by Humphrey method and optical coherence tomography.
- j. FLT3 mutation status will be assessed from bone marrow sample taken at the screening visit. If bone marrow sample is unavailable (e.g., dry tap), the whole blood sample taken at the screening visit will be used. Subjects must be screened by the central laboratory. All subjects including those with rapidly proliferative disease must have screening sample sent to the central lab. If central result is negative, central FLT3 testing can be repeated during screening period.
- k. Bone marrow samples are required during screening, cycle 2 day 1 and cycle 3 day 1. For subjects who do not achieve a CRc (CR, CRp or CRi), the bone marrow assessments will be repeated at day 1 of every 2 subsequent cycles. For subjects who achieve a CRc (CR, CRp or CRi), bone marrow sampling will be repeated on 1 month after the date of remission and every 3 subsequent cycles or if there is suspicion of relapse in the whole blood. Bone marrow samples are also required at the pre-HSCT visit/end of treatment visit and as clinically indicated. If bone marrow aspirate is unobtainable (e.g., dry tap), an additional EDTA tube of whole blood should be collected instead. Bone marrow aspirate is required, and bone marrow biopsy is preferred. In case of inadequate aspirate, bone marrow biopsy is required.
- 1. PK samples for ASP2215 will be collected on cycle 1 day 1 predose, cycle 1 day 8 predose and at cycle 1 day 15 and day 1 predose of each subsequent cycle (1 hour before drug administration). See Section 7.6 of the protocol.
- m. Whole blood and buccal swab collected at day 1 for optional pharmacogenomic study.
- n. ASP2215 is taken daily at home except for clinic days when it will be taken at the clinic.

Footnotes continued on next page

- o. Chest X-ray (or CT of chest) does not need to be repeated if performed within 2 weeks prior to start of screening.
- p. For the purposes of drug preparation and dispensing activities, IRT transaction may be done prior to the visit and do not need to fall within the protocol visit window.

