- k. For MEC and FLAG-IDA, bone marrow samples are required during screening and cycle 2 day 1. Also, an additional bone marrow sample is required at cycle 1 day 15 or later, per institutional guidelines, to assess the need for a second cycle. For LoDAC or azacitidine, bone marrow samples are required during screening, and at cycle 2 day 1 and at cycle 3 day 1. For subjects who do not achieve a CRc (CR, CRp or CRi), the bone marrow assessments will be repeated at day 1 of every 2 subsequent cycles. For subjects who achieve a CRc (CR, CRp or CRi), bone marrow sampling will be repeated at 1 month after the date of remission and every 3 subsequent cycles, or if there is suspicion of relapse in the whole blood. Bone marrow samples are also required at the end of treatment visit and as clinically indicated. If bone marrow aspirate is unobtainable (e.g., dry tap), an additional EDTA tube of peripheral blood should be collected instead. Bone marrow aspirate is required, and bone marrow biopsy is preferred. In case of inadequate aspirate, bone marrow biopsy is required.
- 1. Whole blood and buccal swab collected at day 1 for optional pharmacogenomic study.
- m. LoDAC or azacitidine dosing may continue past cycle 2.
- n. Additional clinic visits are allowed per institutional guideline for subjects receiving MEC (days 1 through 5) or FLAG-IDA (days 1 through 6). MEC and FLAG-IDA are administered for up to 2 cycles depending on response and safety assessments as described in Section 5.1 of the protocol.
- o. Chest X-ray (or CT of chest) does not need to be repeated if performed within 2 weeks prior to start of screening.
- p. For the purposes of drug preparation and dispensing activities, IRT transaction may be done prior to the visit and do not need to fall within the protocol visit window.

Footnotes continued on next page.

- q. Includes Brief Fatigue Inventory, Functional Assessment of Chronic Illness Therapy–Dyspnea-Short Forms, Functional Assessment of Cancer Therapy-Leukemia and dizziness and mouth sores items. The BFI will be administered at cycle 1 day 1 predose, cycle 1 day 8 (± 1 day), day 15 (± 1 day), cycle 2 day 1 (± 2 days), day 15 (± 1 day) and all subsequent cycles day 1 (± 2 days). Functional Assessment of Chronic Illness Therapy–Dyspnea-Short Forms, Functional Assessment of Cancer Therapy-Leukemia and dizziness and mouth sores items will be administered at cycle 1 day 1 predose, cycle 2 day 1 (± 2 days) and all subsequent cycles day 1 (± 2 days).

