Subjects who have a donor identified and achieve a response allowing them to undergo HSCT per each institution's assessment can undergo HSCT without leaving the study. However, ASP2215 should be stopped and a pre-HSCT visit should be performed prior to starting the conditioning regimen for HSCT. ASP2215 can be resumed after stem cell transplantation if the following conditions are met:

- Subject is between 30 60 days post HSCT
- Subject has had successful engraftment as demonstrated by absolute neutrophil count $(ANC) \ge 500/mm3$ and platelets $\ge 20000/mm3$ without transfusions
- Subject does not have \geq grade 2 acute graft-versus-host-disease (GVHD)
- Subject is in CRc

For subjects resuming treatment, subjects will follow the procedures listed under subsequent cycles day 1 in the Schedule of Assessments. Subjects who do not resume ASP2215 will be followed for OS endpoint.

After treatment discontinuation, subjects will have a pre-HSCT/end of treatment visit within 7 days after treatment discontinuation, followed by a 30-day follow-up visit in which a telephone contact with the subject is sufficient unless any assessment must be repeated for resolution of treatment-related AEs. After which the subjects will enter the long-term follow-up period for collection of patient reported outcome (PRO) using EQ-5D-5L, subsequent AML treatment, remission status and survival (cause of death and date of death). The long-term follow-up will be every 3 months, for up to 3 years from the subject's end of treatment visit.

Two interim analyses by an Independent Data Monitoring Committee (IDMC) will be conducted. The first interim analysis is planned when approximately 141 subjects are randomized into ASP2215 arm and at least 112 days (4 treatment cycles) post first dose or randomization (for subjects who received no study drug). The first interim analysis will be performed to evaluate the efficacy endpoint of CR/CRh rate and the study conduct will not be impacted by the result of the CR/CRh rate.

The second interim analysis will be performed when approximately 50% of the planned total number of deaths (death events =129 of planned 258 death events) by any cause have occurred. The second interim analysis will be utilized to determine whether the study should be terminated earlier than planned if ASP2215 has more favorable or harmful outcome than

the salvage chemotherapy group. Details of the interim analyses are described in Section 7.10.

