Disease assessment date refers to the date of central bone marrow aspiration or biopsy assessment. In the event that central bone marrow assessment is not performed or bone marrow is not adequate, local bone marrow assessment date will be used. If no aspirate or biopsy is available and subject is evaluated based on blast count from peripheral blood the date the peripheral blood sample is drawn will be used. If none of the above is available and subject is evaluated based on the presence of extramedullary leukemia, the assessment date of extramedullary leukemia will be used.

The following sensitivity analyses for EFS will be conducted:

- EFS will be defined similarly as the above primary analysis, however the date of the first new anti-leukemia therapy or the last treatment evaluation (when new anti-leukemia therapy date is not available), will be used as the event date of treatment failure.

- Sensitivity analysis of EFS will be performed to evaluate the impact of loss to follow-up on EFS. EFS will be defined similarly as the above primary analysis, however, subjects who discontinue the treatment due to "Lost to follow up" will also be considered as an EFS event (See Section 7.4.3.1 for details of "Lost to follow up" event), and the event date is withdrawal date or last evaluation date as collected on end of treatment, end of 30-day follow up, and end of long-term follow up CRF page whichever occurs first.
- EFS will be defined similarly as the above primary analysis with the following differences:
 - Subjects who discontinue the treatment and achieve best response of NR only will be defined as treatment failure and the event date is the randomization date
 - Subjects who discontinue the treatment and achieve best response of CR, CRp, CRi or PR and experience relapse will be defined as relapse and the event date is the date of first NR after CR, CRp, CRi or PR.
- EFS will be defined similarly as the above primary analysis, however, subjects who discontinue the treatment with post-treatment disease assessment and achieve best response of PR, NR or NE will be defined as treatment failure and the event date is the randomization date.
- Complete remission (CR) rate

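### LFS counts deaths without a time limit but censors survivors at their last disease assessment, so censoring is informative once assessments stop; the size and direction of the bias are not fixed by the SAP

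*SAP*

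**What the plan says.** SAP Section 6.1.3.2 runs LFS from first CRc "until the date of documented relapse (excluding relapse from PR) or death for subjects who achieve CRc". No limit is set on how long after the last dose or assessment a death may fall. For everyone else, "For a subject who is not known to have relapsed or died, LFS is censored on the date of last relapse-free disease assessment date".

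Section 6.1.3.1 fixes the date: "Disease assessment date refers to the date of central bone marrow aspiration or biopsy assessment", with local marrow, then peripheral blood, then extramedullary assessment as fallbacks. A telephone contact is not on the list.

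The last scheduled marrow is at the end of treatment. For ASP2215, Section 2 says "Bone marrow samples are also required at the pre-HSCT visit/end of treatment visit and as clinically indicated"; for chemotherapy, "Bone marrow samples are also required at the end of treatment visit and as clinically indicated". MEC and FLAG-IDA last at most 2 cycles. ASP2215, LoDAC and azacitidine continue to a discontinuation criterion (Section 3.2.1). After HSCT, "Subjects who do not resume ASP2215 will be followed for OS endpoint".

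Long-term follow-up runs every 3 months for up to 3 years after the end of treatment visit. It covers, among other items, "subsequent AML treatment, remission status and survival (cause of death and date of death". The SAP does not say whether remission status from these contacts dates a relapse or extends LFS censoring.

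Section 7.4.3.2 analyses LFS by stratified log-rank test, hazard ratio and Kaplan-Meier median, with no LFS sensitivity analysis. Among the duration endpoints, one sensitivity analysis has the same form: "Duration of CR/CRh will be defined similarly as the above, however deaths without report of relapse are considered as events".

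**The concern.** Take two remitters whose last marrow is 2 months after CRc, both contacted at month 14. One died at month 13 and contributes 13 months at risk and an event. The other is alive and contributes 2 months. Whether a subject was at risk between months 2 and 13 is thus decided by what happened afterwards. Kaplan-Meier and log-rank methods require that it is not.

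This differs from imperfect detection of relapse: it would arise even if nobody relapsed. Other endpoints in the SAP avoid it. EFS counts deaths only within 30 days after the last dose, and duration of CRc censors deaths at the last assessment, as it does survivors.

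At stake are the reported LFS median, hazard ratio and p-value. Assessment length differs by regimen, so the distortion need not cancel between arms.

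**Working it through.** The SAP gives no planning figure for LFS, so there is none to reproduce. Every input below is an assumption unless a section is named.

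**1. No relapse, one arm.** Exponential survival from CRc with median 12 months, last marrow at 2 months, cutoff uniform over 6 to 24 months. Under the SAP rule the LFS median is 6.3 to 6.4 months and 12-month LFS is 18%. Censoring at last contact returns 12 months and 50%.

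**2. No relapse, two arms with identical survival.** Median 14 months, 110 v 35 remitters; those stopping early do so at 2 months (control) or 3 months (ASP2215). The table shows how often the log-rank test favours ASP2215 at two-sided 0.05 (nominal 2.5%), as ranges over repeat simulations.

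| Stopping early, control v ASP2215 | False significance |
|---|---|
| 80% v 30% | 39-41% |
| 80% v 50% | 23-25% |
| 60% v 30% | 16-18% |
| 60% v 50% | 7-8% |
| 50% v 50% | about 4% |

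With last-contact censoring the same test gives 3.7%, so the last row is close to no effect. The remitter numbers matter. The CR rates in Section 4 imply 0.25 × 246 = 61.5 and 0.10 × 123 = 12.3 subjects (CRc is broader). With 62 v 12 the first four rows span about 7-20%.

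**3. Relapse added.** Median time to relapse 6, 12 or 18 months; death without relapse 36 months; death 4 months after relapse; cutoff uniform over 6 to 36 months. With competing exponential times the true LFS median is a·36/(a + 36): 6·36/42 = 5.1, 12·36/48 = 9.0, 18·36/54 = 12.0. Marrow follow-up is 1 to 3 months (short) or exponential with median 6 or 12 months (long).

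| True median | Captured, short | Captured, long | Not captured, short |
|---|---|---|---|
| 5.1 | 4.6 | 4.9-5.0 | 7.4 |
| 9.0 | 6.6 | 7.8-8.3 | 9.2-9.3 |
| 12.0 | 7.6-7.7 | 9.6-10.5 | 9.9-10.0 |

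"Captured" means that relapses after treatment enter the data. In the short group every subject at risk beyond 6 months goes on to an event; in the long groups 58-86% do. With a true hazard ratio of 1.0 and all controls in the short group, the SAP rule gives 0.68-0.90 (captured) or 0.77-1.12 (not captured).

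**4. Candidate repairs, same inputs.** True hazard ratio 1.0, short v long with median 12 months, assessment treated as continuous until it ends.

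| Rule | Hazard ratio |
|---|---|
| Deaths and relapses after the last assessment not counted | 1.00-1.01 |
| Deaths counted to 1 month after, survivors censored at last assessment | 0.82-0.91 |
| Same, 2 months | 0.62-0.78 |
| Same, two scheduled intervals (2 × 3 cycles × 28 = 168 days, about 5.5 months) | 0.38-0.65 |
| Deaths and survivors both followed to the end of the window, relapse captured | 1.01-1.02 |
| Same, relapse not captured | 1.26-1.53 |
| Last contact, relapse captured | 1.00-1.01 |
| Last contact, relapse not captured | 1.17-1.33 |

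A window that applies to deaths alone keeps the fault inside the window. Last-contact censoring without relapse capture overstates LFS (13.3 v true 9.0 months in the short group).

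**The case against.** A reader might infer that LFS is badly understated, that only subjects who will die remain at risk, and that the rule manufactures an ASP2215 benefit. The documents do not support that much.

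- **Direction.** Consistent understatement needs post-treatment relapses to be captured, which the SAP leaves open. If they are missed, the later death stands in for the relapse, and the median can be right or too long. With relapse added (median 6 months), false significance in the 110 v 35 setting falls to 5-11% if captured and 2-3% if not; with median 12 months it is 6-27% and 4-11%.
- **Risk set.** Subjects still assessed on treatment stay properly at risk. Marrows are also taken when clinically indicated, and blood or extramedullary assessments can count.
- **Arm contrast.** LoDAC and azacitidine are open-ended like ASP2215, and stopping for HSCT without resuming happens in the ASP2215 arm. The SAP gives neither the high-intensity share among remitters nor the share stopping early.
- **Weight.** LFS is an other secondary endpoint outside the OS-EFS-CR sequence. Duration of CRc, in the same remitters, treats deaths and survivors alike. The affected CR/CRh duration analysis is only a sensitivity analysis.

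All of this stands and limits the claim about size. None of it makes the censoring independent.

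**Conclusion.** The LFS definition has a real flaw: after scheduled assessments stop, censoring depends on later survival, and no rule or LFS sensitivity analysis in the SAP repairs it. The death-counting analysis of CR/CRh duration shares it.

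The size is conditional. With post-treatment relapses captured, LFS is understated, slightly to substantially, and a null hazard ratio can read 0.68-0.90 if all controls stop early, which is an upper case. Without capture the direction is open. False significance of about 8-40% holds only with no relapse, 110 v 35 remitters and 60-80% v 30-50% stopping early. An arm imbalance is plausible because MEC and FLAG-IDA end after at most 2 cycles, but the SAP does not quantify it. Error control for OS, EFS and CR rate is untouched. This is a should-fix point.

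**What to change.** In Section 6.1.3.2, give each remitter one closing date for LFS and apply it to relapse, death and censoring alike.

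- **Main rule.** Count a death only while the subject is under scheduled assessment. Censor later deaths at the last relapse-free assessment, as survivors are, and do not count later relapses.
- **If a window after the last assessment is preferred** (for example two scheduled intervals), state its length in advance and carry subjects known alive and in remission to its end too. This needs relapse to be captured within the window. A window for deaths alone is not a cure.
- **Sensitivity analysis.** Censor at the last date known alive and in remission, with a stated rule for using long-term remission status both to date relapse and to extend censoring. Do not simply censor at last contact.
- **CR/CRh duration.** Apply the same rule to the sensitivity analysis that counts deaths.

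Cost: wording, one derived date, fewer LFS events, and a curve that ends early for short regimens, possibly before the median. Efficacy was reported at the 17 SEP 2018 cutoff and version 4.0 plans no further efficacy analysis. The practical step is therefore a supplementary re-analysis of existing data, or a stated limitation wherever LFS is reported.

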6.4 Other Variables

Duration of exposure

Duration of exposure to each component of a study drug will be calculated in days, using the following formula:

Last date of exposure – First dose date + 1 – (on-study HSCT period for subjects undergo on-study HSCT)

For ASP2215, last date of exposure = last dose date of ASP2215

For chemotherapy, last date of exposure = (initial dose date of the last cycle +28-1) or death date if death occur within last cycle

When the start or stop date is missing, then the exposure will be treated as missing.

Duration of exposure for a chemotherapy regimen, i.e. MEC and FLG-IDA, will be the maximum (duration of exposure of all treatment components).

When the last date of exposure is beyond cutoff date, the cutoff date will be used as the last date of exposure.

Number of dosing days

Number of days with non-zero dosing.

Number of cycles

Number of cycles for each component of study drug refers to total number of cycles with non-zero dosing in the cycle.

Number of cycles for a chemotherapy regimen refers to total number of cycles with non-zero dosing of any treatment component in the cycle.

• Cumulative dose (dose unit)

Cumulative dose will be calculated using the following formula for each type of study drug:

- ASP2215: Sum of [(stop date start date + 1) * dose captured on dosing CRF] across all records
- LoDAC: Sum of (number of dose taken * 20mg) across all records and all cycles.
 If number of dose take is "unknown", it will be treated as missing.
- Azacitidine: Sum of (number of dose taken * actual delivered dose captured on dosing CRF) across all records and all cycles. If number of dose taken is "unknown", it will be treated as missing.

 Each component of MEC and FLAG-IDA: Sum of (actual delivered dose captured on dosing CRF) across the days when study drug was administered. If answer to "entire infusion administered" is No, actual delivered dose will be treated as missing.

• Average daily dose (dose unit/days)

Cumulative dose (dose unit)

Number of dosing days (days)

Dose intensity

Dose intensity will be calculated in mg/day for ASP2215 as:

Cumulative dose (mg)

Duration of exposure (days)

Dose intensity will be calculated in dose unit/cycle for chemotherapy as:

Cumulative dose (dose unit)

----- x 28 (days/cycle)

Duration of exposure (days)

• Relative dose intensity

Relative dose intensity for ASP2215 will be calculated as:

Dose intensity (mg/day)

-----x 100%

120 (mg/day)

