For subjects that undergo HSCT without leaving the study and plan to resume ASP2215 treatment after HSCT, concomitant transfusion is defined as transfusion received between the date of first dose (inclusive) and the date of last dose (inclusive) before pre-HSCT visit, or between resumption of ASP2215 (inclusive) and the date of last dose (inclusive).

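### The post-baseline transfusion period does not exclude the off-drug HSCT interruption, so off-drug days after transplant count toward the 56 transfusion-free days credited to ASP2215

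*SAP*

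**What the plan says.** SAP Section 6.1.3.2 defines the window: "Post-baseline period is defined as the period from 29 days post first dose until last dose". A subject with enough time on treatment ("For subjects who are on treatment >=84 days") is "classified post-baseline transfusion independent if there is one consecutive 56 days without any RBC or platelet transfusion within post-baseline period". The section makes no mention of HSCT. It also limits the endpoints to one arm: "Transfusion conversion rate and transfusion maintenance rate will only be defined for subjects in ASP2215 arm".

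Section 3.2.1 explains why this matters. For subjects going to transplant, "ASP2215 should be stopped and a pre-HSCT visit should be performed prior to starting the conditioning regimen for HSCT". Drug may be resumed 30 to 60 days after HSCT if there is engraftment, no acute GVHD of grade 2 or higher, and CRc. The last dose can therefore fall well after the transplant.

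Elsewhere the SAP deals with the interruption explicitly:

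- **Exposure (Section 6.4):** the formula subtracts the "on-study HSCT period for subjects undergo on-study HSCT".
- **Concomitant transfusion (Section 6.4):** for subjects who plan to resume, only transfusions "between the date of first dose (inclusive) and the date of last dose (inclusive) before pre-HSCT visit, or between resumption of ASP2215 (inclusive") and the last dose are counted. Concomitant medication follows the same pattern.
- **TEAEs (Section 6.2):** the window is split, closing 30 days after the last dose before the pre-HSCT visit and reopening at resumption.

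**The concern.** Transfusion conversion and maintenance are secondary efficacy endpoints reported for ASP2215 alone, so no control arm can show what transplantation contributes. Under the written rule, transfusion-free days that a resumer spends off drug with a new graft count as evidence of independence on ASP2215.

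Two gaps in the wording add to this. Section 6.1.3.2 does not say whether time on treatment includes the interruption, although exposure in Section 6.4 is net of it. Nor does it name the transfusion records to be used. If a programmer used the concomitant-transfusion variable, transfusions in the gap would disappear while the gap days stayed in the window.

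OS, CR/CRh and CR each have a sensitivity analysis that censors at HSCT or stops before it (Sections 6.1.1, 6.1.2 and 6.1.3.1). The only sensitivity analysis for the transfusion rates recodes not-evaluable subjects as dependent.

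**Working it through.** **1. The plan's threshold.** 28 baseline days + 56 = 84. A window from Day 29 to Day 84 has 84 − 29 + 1 = 56 days, so the 84-day rule reproduces. If 29 days after first dose is read as Day 30, 84 − 30 + 1 = 55 days remain. That is a one-day ambiguity and a side point.

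**2. Off-drug days after transplant that count, with gap transfusions included.** Let resumption be at HSCT+h (h from 30 to 60, Section 3.2.1) and the last transfusion at HSCT+t (t assumed).

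- Off-drug transfusion-free days = h − t − 1.
- On-drug days still needed = 56 − (h − t − 1), or 0 if negative.

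| h | t | Off-drug days counted | On-drug days needed |
|---|---|---|---|
| 30 | 0 | 29 | 27 |
| 45 | 0 | 44 | 12 |
| 60 | 0 | 59 | 0 |
| 60 | 3 | 56 | 0 |
| 60 | 10 | 49 | 7 |
| 60 | 20 | 39 | 17 |

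For all 56 days to fall off drug and after transplant, h must be at least 57 + t. That is possible only for resumption between HSCT+57 and HSCT+60, with the last transfusion by HSCT+3 at the latest.

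**3. A subject who becomes independent through the gap (assumed timeline).** Last pre-HSCT dose Day 80, HSCT Day 90, resumption Day 150, last dose Day 169. On-drug days net of the gap are 80 + 20 = 100. Transfusions fall every 10 days to Day 71, then on Days 85, 92, 97 and 105.

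- As written: Days 106 to 169 = 64 days, so independent. Of these, Days 106 to 149 = 44 are off drug.
- Gap removed, runs not joined: longest run Days 150 to 169 = 20 days, so dependent.
- As written, using concomitant transfusions only: Days 72 to 169 = 98 days, so independent.

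Using concomitant transfusions only, the gap alone supplies a + h − 1 apparently transfusion-free days, where a is the time from last dose to HSCT. The SAP does not give a. For an assumed 1 to 14 days, the range is 1 + 30 − 1 = 30 to 14 + 60 − 1 = 73.

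**4. A subject affected the other way (assumed timeline).** Baseline dependent, last pre-HSCT dose Day 70, no transfusion on Days 29 to 70, HSCT Day 80, transfusions from Day 72 to Day 110, resumption Day 140, last dose Day 150. On-drug days net of the gap are 70 + 11 = 81.

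- As written: the window contains transfusions, and its longest runs are Days 29 to 71 = 43 and Days 111 to 150 = 40. The subject is dependent whether time on treatment is counted gross (150) or net (81).
- Gap removed, net count: fewer than 84 days and no transfusion in the window, so not evaluable and out of the denominator.

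**5. Direction.** With at least 84 on-drug days net of the gap, adding gap days to the window can lengthen the longest run but never shorten it. Any reclassification is then toward independent. Below 84 net days, a gap transfusion can turn not evaluable into dependent, as in step 4, which lowers the rate.

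**The case against.** The strongest reply has four parts.

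- **Gap transfusions count.** The rule asks for 56 days without any transfusion, not without a concomitant one. The baseline period reaches back 28 days before first dose, so the derivation cannot rest on the concomitant variable alone. This stands. A reader might infer that late resumers qualify on the gap by itself; that holds only if gap transfusions are ignored, which the text does not direct.
- **The direction is not uniform.** A reader might infer that both rates are inflated. The documents do not support this: step 4 shows the opposite movement for subjects with under 84 net on-drug days.
- **No percentage-point effect can be stated.** The SAP gives neither the number of resumers nor the number of evaluable subjects. Some resumers will also have a qualifying run on drug. This stands.
- **Ending the main analysis before HSCT is a preference.** It would discard on-drug time after resumption. Section 6.4 keeps both on-drug segments for concomitant medication and transfusion, and the SAP puts pre-HSCT views of efficacy in sensitivity analyses. This also stands and shapes the fix.

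None of this removes the core point. Reading last dose as the last dose before HSCT is not tenable, because Sections 6.2 and 6.4 spell that out where they mean it.

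**Conclusion.** The point holds as a defect in a stated rule. For ASP2215 subjects who resume after HSCT, Section 6.1.3.2 counts off-drug, post-transplant days toward independence, in conflict with the SAP's own treatment of that interval in Sections 6.2 and 6.4. Per subject, up to 29, 44 or 59 such days can count for resumption at HSCT+30, +45 or +60, taking the last transfusion as the day of transplant. The typical case is a run straddling resumption; a run wholly off drug and after transplant needs resumption near the end of the window. The problem grows if only concomitant transfusions are used.

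The net effect on the two rates is unknown in size and sign. The consequence is confined to descriptive secondary estimates with confidence intervals (Section 7.4.3.2). No test, alpha, power or interim decision depends on them.

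**What to change.** In Section 6.1.3.2:

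1. Remove the HSCT interruption from the post-baseline period, from the day after the last dose before the pre-HSCT visit until ASP2215 is resumed.
2. State that a 56-day run may neither include days of the interruption nor be joined across it.
3. Count time on treatment net of the interruption, by cross-reference to duration of exposure in Section 6.4.
4. Name the transfusion records used.
5. Add a sensitivity analysis that ends the period at the last dose before the pre-HSCT visit, parallel to the pre-HSCT analyses of CR and CR/CRh.

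The plan should also say how to class a subject whose two on-drug segments total at least 84 days but neither of which contains 56 post-baseline days.

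The cost is SAP wording and reprogramming from dates that Section 6.4 already uses. Some subjects may change to dependent or not evaluable. Version 4.0 plans no further efficacy analysis (Sections 1 and 6.1), so the rates in the primary report would have to be rerun and the change justified in the CSR.
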